Stanford U19 CCHI. Project 2: Innate and Acquired Immunity to Influenza Infection and Immunization (Under grant 'Adaptive and Innate Immunity, Memory and Repertoire in Vaccination and Infection'); SLVP029.
V2.0_07AUG2015

OHSR	Office for Human Subjects Research
ORA	Office of Regulatory Affairs, DMID, NIAID, NIH, DHHS
PHI	Protected Health Information
PI	Principal Investigator
PK	Pharmacokinetics
QA	Quality Assurance
QC	Quality Control
SAE	Serious Adverse Event/Serious Adverse Experience
SLVP	Stanford-LPCH Vaccine Program
SMC	Safety Monitoring Committee
SOP	Standard Operating Procedure
TIV	Trivalent inactivated influenza vaccine
US	United States
WHO	World Health Organization

PROTOCOL SUMMARY

Title: Project 2: Innate and Acquired Immunity to Influenza Infection and Immunization	
Number of Sites: 1	
Study Duration: 5 years for enrollment, vaccination, analysis	
Subject Participation Duration: 4-5 weeks	
Description of Agent or Intervention: Quadrivalent, Live Attenuated Influenza Vaccine (LAIV4) Quadrivalent, Inactivated Influenza Vaccine (IIV4)	
Objectives:	
Primary:
 
 1. To compare the nasal mucosal transcriptional responses to LAIV4 between the following age groups: 2-4 year old children, 9-13 year old children, and 18-49 year old adults 2. To compare the B cell response to LAIV4 between the following age groups: 2-4 year old children, 9-13 year old children, and 18-49 year old adults 3. To investigate the evolution of B cell repertoire in young children after repeated LAIV4 immunization 4. To compare the B cell response to IIV between the following age groups: 6-23 month old children, 9-13 year old children, and 18-49 year old adults 5. To investigate the evolution of B cell repertoire in young children first immunized with IIV followed by repeated LAIV4 immunization. 
Secondary:
 
 1. To compare the B cell repertoire in response to LAIV4 versus IIV in different age groups.

Description of Study Design: This is a Phase IV study of healthy children and adults who will receive the current seasonal influenza vaccine. There are no exclusions for gender, ethnicity or race. The volunteers will be enrolled into one of 7 groups over a 5-year period. Immunization will be at Day 0. Blood and NP swab samples will be collected at various time points based upon group assignment for various immunological assays.

Group A (LAIV4/annual return): Up to six 2-4 year old volunteers will be given a quadrivalent live, attenuated influenza vaccine (LAIV4). Blood samples to conduct the assays described will be taken at Day 0 pre-immunization and Day 6-8 post-Dose 1 for all children irrespective of those who require 1 dose (prior flu vaccination history) or 2 doses (vaccine-naïve). For children requiring 2 doses of vaccine, a second immunization will be given at Day 28-32 after Dose 1. All participants in this group will be asked to return annually for repeat immunization per ACIP guidelines and blood sample collection.

Group B (LAIV4/single year): Up to twenty 2-4 year old volunteers will be given a quadrivalent live, attenuated influenza vaccine (LAIV4). Blood samples to conduct the assays described will be taken at Day 0 pre-immunization and Day 6-8 post-Dose 1 for all children irrespective of those who require 1 dose (prior flu vaccination history) or 2 doses (vaccine-naïve). For children requiring 2 doses of vaccine, a second immunization will be given at Day 28-32 after Dose 1.

Group C (LAIV4/NP swab group/single year): Up to twenty 2-4 year old volunteers will be given a quadrivalent live, attenuated influenza vaccine (LAIV4). NP swabs will be collected at Day 1 and Day 20-22 post-Dose 1 for all children irrespective of those who require 1 dose or 2 doses of vaccine. For children requiring 2 doses of vaccine, a second immunization will be given at least 28 days after Dose 1. No blood will be collected for this group.

Group D (IIV4/annual return): Up to six 6 month-23 month old (inclusive) volunteers will be given a quadrivalent inactivated influenza vaccine (IIV4). Blood samples to conduct the assays described will be taken at Day 0 pre-immunization and Day 6-8 post-Dose 1 for children requiring 1 dose of vaccine (prior flu vaccination history). For children requiring 2 doses of vaccine (vaccine-naïve), a second immunization will be given at Day 28-32 after Dose 1. The second blood sample will be collected on Day 6-8 post-Dose 2. Volunteers will be asked to return annually for repeat immunization per ACIP guidelines and blood sample collection.

Group E (IIV4/single year): Up to twenty 6 month–23 month old (inclusive) volunteers will be given a quadrivalent inactivated influenza vaccine (IIV4). Blood samples to conduct the assays described will be taken at Day 0 pre-immunization and Day 6-8 post-Dose 1 for children requiring 1 dose of vaccine (prior flu vaccination history). For children requiring 2 doses of vaccine (vaccine-naïve), a second immunization will be given at Day 28-32 after Dose 1. The second blood sample will be collected on Day 6-8 post- Dose 2. Volunteers will participate for single year.

Group F (LAIV4/single year) Up to forty 9-13 year old (n= 20) and 18-49 year old (n= 20) volunteers will be given a quadrivalent live, attenuated influenza vaccine (LAIV4). Blood samples and NP swabs will be

[figure not shown]
collected. Blood samples will be taken at Day 0 pre-immunization, Day 6-8 post-immunization and Day 28±4 post-immunization. NP swabs will be collected at Day 1 post-immunization and Day 28 post – immunization. Volunteers will participate for a single year.

Group G (IIV4/single year) Up to forty 9-13 year old (n= 20) and 18-49 year old (n= 20) volunteers will be given a quadrivalent inactivated influenza vaccine (IIV4). Blood samples to conduct assays will be taken at Day 0 pre-immunization, Day 6-8 post immunization and Day 28±4 post-immunization. Volunteers will participate for single year. No NP swabs will be collected for this group.

[figure not shown]
Estimated Time to Complete Enrollment: Participants will be enrolled Aug-Dec in each of 5 years

U19 CCHI Project 2 (SLVP029)

[figure not shown]
Innate and Acquired Immunity to Influenza Infection and Immunization

[figure not shown]
U19 CCHI PROJECT 2 (SLVP029)

U19 CCHI PROJECT 2 (SLVP029)

U19 CCHI Project 2 (SLVP029)

2 BACKGROUND INFORMATION AND SCIENTIFIC RATIONALE

2.1 Background Information

Influenza virus (flu) is a Category C priority human pathogen with a worldwide distribution that is responsible for annual epidemics and intermittent pandemics. The spread of the 2009 swine-origin flu A/H1N1 pandemic and the identification of highly pathogenic avian A H5N1 and H7N9 strains highlight the need for better vaccines. Two types of licensed vaccines are available in the US: trivalent (IIV3, previously TIV) and quadrivalent (IIV4) inactivated vaccines both administered by injection, and nasally administered quadrivalent live, attenuated influenza vaccines (LAIV4) administered by nasal spray. Both vaccines are safe and effective in their approved age groups. LAIV is more efficacious than IIV, especially against mismatched flu strains, in children 6 months to 18 years of age¹⁻³, as well as in a recent study using ferret model³⁵. In adults 18 to 49 years of age, LAIV has been either equally effective or somewhat less effective than IIV^{1,4-5}. In the elderly, IIV has variable but often modest efficacy⁶. Despite extensive investigation of immune responses in infected patients and vaccine recipients, the basis of protective immunity is not fully understood. B cell and antibody (Ab) responses are key components of the adaptive immunity induced by natural (or "wild type", wt) flu infection and vaccination, but conventional measures of serum Ab do not always predict protective efficacy of flu vaccination, especially of LAIV in healthy adults and of IIV in the elderly. A recent study of experimentally infected adults showed that levels of flu-specific CD4 T cells correlated with reduced virus shedding and disease severity⁷, suggesting that preexisting cellular immunity plays a role in modulating viral replication and pathogenesis. In previous studies we showed that LAIV induced greater T cell responses in children than in adults⁸.

The upper respiratory tract (URT) mucosa is the initial replication site of wt flu and LAIV. The nasal mucosa is a complex and well-integrated system that serves as a first line of defense against infection⁹. The URT mucosa contains several types of epithelial cells thought to be the targets of initial infection by respiratory viruses including flu¹⁰. In a recent study, nasal swab specimens from flu patients were successfully used to identify lipid mediators that both induce and resolve local inflammation¹¹. Previous studies have shown robust innate immune responses in primary human alveolar and bronchial epithelial cells infected by flu *ex vivo*¹²⁻¹⁴. Studies in mice and humans suggested that early innate immune responses help shape subsequent adaptive responses. This is supported by the finding that the magnitude and persistence of Ab responses, as well as subsequent recall responses, to a live attenuated yellow fever vaccine correlate with early innate immune transcriptional responses¹⁵⁻¹⁶ and likely involve multiple toll-like receptors that stimulate production of proinflammatory cytokines¹⁷⁻¹⁸.

Animal studies have shown that type I interferon (IFN) responses elicit rapid and significant amounts of antigen (Ag)-specific IgG2c predominantly from follicular B cells¹⁹, and are important for the optimal priming, expansion, and memory formation of T cells after flu infection²⁰⁻²¹. We recently found that rotavirus (RV) infection of intestinal enterocytes *in vivo* results in distinct transcriptional responses in infected vs. bystander uninfected epithelial cells and that most of the early IFN response to infection occurs in a nonepithelial immune cell compartment²². We also found that the local IgA B cell response to RV infection is promoted by plasmacytoid dendritic cells (DCs), a major producer of IFN during the early RV infection in both mice and humans²³. These findings support the notion that early local innate immune responses, characterized by the robust induction of IFN and/or other cytokines, in the flu-infected nasal mucosa are likely to have a profound effect on viral replication and on subsequent virus-specific adaptive responses. This hypothesis will be tested in proposed experiments to examine the crosstalk between nasal epithelial and immune cell subsets, the effects of preexisting acquired immunity on this crosstalk, and the modulating effect the crosstalk has on viral replication and subsequent acquired immunity, presumably because children have lower levels of pre-vaccination immunity, resulting in higher levels of LAIV replication and subsequent T cell responses. The exact mechanisms linking preexisting immunity to local flu replication and subsequent immune responses are not clear.

The URT mucosa also hosts multiple resident professional Ag presenting cells and Ag-specific lymphocytes critical for adaptive and innate immune responses. These cells, including DCs, natural killer (NK) cells, and memory and effector B and T cells (including those specific for flu), can be collected using flocked nasopharyngeal swabs²⁴⁻²⁵. The outcome of LAIV immunization in flu-experienced older children and adults is likely strongly influenced by pre-existing flu-specific resident memory T and B cells in addition to the local innate responses. However, human URT resident immune cells have not been extensively studied and their role in controlling local flu replication as well as their relationship with local innate responses are unclear, largely due to difficulties in access and isolation of sufficient numbers of nasal cells for analysis. Defining the roles of these early adaptive immune cell responders to natural (or "wild-type", wt) flu and LAIV infection in the URT will be an important step toward identification of the modulators of local replication and immunity.

Ideally, a flu vaccine should induce protective immunity not only to homologous vaccine Ags but also to heterovariant strains or antigenically drifted new flu Ags. LAIV is clearly more effective at inducing protection against both antigenically matched and mismatched strains than IIV, especially in children^{1,3}. However the basis for the enhanced induction of heterovariant protective immunity following infection (vs. parenteral vaccination) is not understood. It is not known whether heterovariant Ab reactivity is mediated by the same Ab molecules that recognize both homotypic and variant epitopes of different strains, or by different Ab molecules each targeting a cognate Ag on a specific variant strain. This question cannot be easily addressed with serum samples and conventional serologic assays. IIV induces a higher titer serum Ab

response than LAIV in adults and older children, but one year after vaccination with either LAIV or IIV the levels of flu-specific circulating memory B cells are similar²⁶. This indicates that convalescent serum Ab titers do not give a complete picture of B cell mediated immunity following vaccination.²⁶⁻³² and infection^{30, 33-34}. We and others have studied the B cell response to flu vaccination by examining the acute circulating plasmablast (PB) response. Analysis of this response provides a snapshot of the overall B cell response to recent Ag exposure without the confounding effects of preexisting circulating Abs. Analysis of the PB Ab repertoires revealed that the B cell response of adults to flu vaccination is largely a recall response of pre-existing memory B cells²⁸. In preliminary studies, we identified flu-specific PBs that recognized previously circulated flu viruses better than current vaccine strains. These observations suggest that both the quantitative and qualitative nature of the B cell response to a new flu vaccination or to infection in the flu-experienced individuals is fundamentally shaped by the pre-vaccination memory B cell repertoire. However, factors that initially establish this repertoire and the evolution of this repertoire during repeated exposure to influenza antigens, especially during repeated immunization with different types of influenza vaccines, the mechanism of its regulation, and the impact of initial Ag exposure on subsequent flu immunity in different age groups are unknown.

2.2 Rationale

Our previous studies have focused on vaccine-induced immunity to influenza (flu); we have examined systemic humoral and cellular responses, as measured by levels of circulating and plasmablast-derived antibodies (Abs), T cells, B cells and natural killer cells, to identify determinants of immunity following intranasally-administered live attenuated (LAIV) and parenterally administered inactivated flu vaccines (IIV). The mechanistic basis for variable rates of protective immunity induced by vaccination – especially heterotypic immunity induced by LAIV in children and decreased immunity observed upon vaccination of the elderly with IIV – remains poorly understood. The upper respiratory tract (URT) is the initial site of replication of natural (or “wild type”, wt) flu and LAIV strains. We hypothesize that key determinants of flu immunity are regulated at the URT level and can be understood by careful examination of virus-host interactions at the local level. These local determinants include early host antiviral innate responses, tissue-resident immune cells, and viral replication levels. We have initiated studies of early innate and acquired immune responses in primary human nasal cells collected either directly from patients acutely infected with influenza or subjects who had received LAIV, and in primary URT nasal cells acutely infected with wt flu or LAIV strains.

As a second approach to better understanding flu immunity, we have examined B cell and Ab responses to flu vaccination with a focus on qualitative and quantitative differences in responses between old and young vaccinees, IIV and LAIV recipients, and heterovariant vs. homotypic Ab reactivities. We propose to extend these studies using a

novel barcoding technology for high-throughput analysis of immunoglobulin (Ig) repertoires in flu-specific plasmablasts focusing on the initial responses to IIV vs. LAIV in influenza-naïve children. Evolutionary trees of Ab repertoires will be generated allowing us to identify – in an unbiased manner – affinity-matured clonal Ig families that are likely critical components of the flu Ab response. By expressing representative Ig genes from these clonal families, their functional property and homotypic vs. heterovariant specificity will be characterized.

Based on these two complementary research goals, we hypothesize the following: Infection of the URT with LAIV4 or wt virus triggers hierarchical transcriptional signatures in local resident epithelial and immune cells that regulate viral replication and subsequent immunity. We will collect NP swab specimens from recipients of LAIV4 and examine selected early transcriptional responses and viral replication levels in epithelial and lymphocytic cells (collection of the samples from subjects infected with the wild-type influenza virus will be completed by enrolling volunteers under a separate protocol). Host transcriptional responses and viral replication will be measured in bulk tissue, purified epithelial and lymphocyte cells, and single infected and bystander (non-infected) cells using flow cytometry and qRT-PCR. We predict that LAIV4 and wt virus will induce overlapping but clearly distinct transcriptional and phosphorylation signatures. In the older children and adult subjects from whom both NP swab and blood samples will be collected, we will also test whether local antiviral transcriptional responses and viral replication levels correlate with subsequent flu specific immune responses and will identify early local transcripts that predict subsequent B and T cell immunity in vivo.

We also hypothesize that: The antigen-specific Ig repertoires elicited by infection with wt flu virus or LAIV4 vs. immunization with inactivated flu vaccine (IIV4) are quantitatively and qualitatively distinct, especially in young children undergoing the first or second exposure to flu antigens, and are different from those in flu-experienced adults in terms of number, size, Ig gene usage, and isotype of clonally expanded Ig gene families, and in levels of somatic hypermutation and heterovariant cross-reactive Ab activity. We predict these differences have the potential to affect the evolution of an individual's immune response to novel flu antigens. In this protocol, we will examine these characteristics in LAIV4-infected vs. IIV4-exposed young children 6 months to 4 years of age who are influenza-naïve (or almost naïve) and compare them to children 9 – 13 years old and adults using a novel barcoding-based amplification and sequencing technology. These differences are predicted to shape the subsequent Ab and memory B cell responses, in particular their ability to recognize heterovariant strains.

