8.2 Laboratory Evaluations

8.2.1 Special Assays or Procedures

Subject Analysis – We will use CyTOF mass cytometry to determine the precise number of each white blood cell type in a given patient sample and their activation state and function (B cells, T cells, NK cells, T cells, monocytes, dendritic cells).

Gene Expression Analysis– We will collect part of the blood sample in a PAXgene tube and prepare probes from the mRNA for gene expression analysis using Agilent microarrays that survey global gene expression. This will tell us if there is a particular gene expression signature.

Serum Cytokine Analysis – As there have been reports of changes in the serum cytokine repertoire in older people, we will survey serum samples for different cytokines using the Panoics/Luminex system now running the Human Immune Monitoring Center at Stanford.

Responses to Cytokine Stimulation – We will stimulate PBMCs with various cytokines and will analyze the phosphorylation status of different STATs and other key mediators of cellular activation in B cells, T cells and monocytes by flow cytometry.

HAI Antibody Titer – The standard HAI antibody assay will be run on samples at baseline and Day 28 or other study visit to evaluate the duration of response to vaccination.

Sequencing of TCR $\alpha\beta$ and Immunoglobulin Genes– We will sort B and T cells and sequence their antibody repertoires.

Host transcriptional response - We will carry out quantitative real time PCR analysis to determine the levels of specific transcripts in bulk and sorted nasal cell populations.

Antibody reactivity – We will generate plasmablast-derived polyclonal antibodies (PPAb) and recombinant mAbs and determine their reactivity against influenza antigens of the vaccine and variant strains by ELISA and SPR assays.

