10.3 Final Analysis Plan

In this proposal, the host innate immune responses to influenza virus infection will be examined within flow cytometry defined subsets of primary infected and bystander cells, as well as in bulk nasal mucosa RNA preparations. We have recently developed statistical models and methods that are appropriate to analyze transcriptional profiles following viral infection in high dimensional datasets. The basic approach that we propose is to obtain bulk measures at different hierarchical levels of the human nasal mucosa, including from sorted bulk populations and single cells from selected populations, and to identify significant innate response transcriptional signatures in the different age groups. Detailed procedures and analysis routines for analysis have been published recently and will be followed³⁶

We will obtain sequences of cognate heavy- and light-chain pairs and determine their V(D)J usage by analyzing them with IMGT HighV-QUEST. The heavy and light chains will be grouped according to their V-gene usage to clonal families of antibodies that use the same heavy-chain V(D)J and light-chain VJ sequences. Antibody phylogenetic trees will be generated based on the Ig sequences. The number, size, Ig gene usage, and isotype of clonally expanded Ig gene families, and in levels of somatic hypermutation and heterovariant cross-reactive Ab activity will be compared between the different vaccines and age groups.

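### The planned Group F link between nasal signals and later immunity gives Day 0 immunity no role, so it cannot separate a local determinant from a marker of prior immunity

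*Combined protocol and SAP*

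**What the plan says.** Section 2.2 states that, in participants with both nasopharyngeal swabs and blood, the study will "test whether local antiviral transcriptional responses and viral replication levels correlate with subsequent flu specific immune responses". A second aim given there is to find nasal transcripts, measured early, that foretell later B and T cell responses. Only Group F fits that description: up to 20 people aged 9-13 and up to 20 aged 18-49, with swabs at Day 1 and Day 28 and blood at Day 0, Day 6-8 and Day 28 (Section 4).

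Section 10.3 does not take this analysis up. For the nasal data it says only that the study will "identify significant innate response transcriptional signatures in the different age groups". For the repertoire data it compares vaccines and age groups.

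On prior immunity, Section 2.1 makes four statements:
- It offers the explanation "presumably because children have lower levels of pre-vaccination immunity, resulting in higher levels of LAIV replication and subsequent T cell responses", and adds that the mechanisms are not clear.
- It says "The outcome of LAIV immunization in flu-experienced older children and adults is likely strongly influenced by pre-existing flu-specific resident memory T and B cells".
- It describes the B cell response in flu-experienced people as shaped by the memory B cells they already carry.
- It lists "the effects of preexisting acquired immunity on this crosstalk" among the things to be examined, without a method.

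A systemic baseline measure is already planned. Section 8.2.1 says "The standard HAI antibody assay will be run on samples at baseline and Day 28".

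**The concern.** If prior immunity influences both the Day 1 nasal measure and the later systemic response, the two will correlate even when neither affects the other. Stratifying by age does not remove this. The limits on earlier influenza vaccination do not apply to Group F (Sections 5.1 and 5.2), so prior immunity can differ widely within an age stratum.

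Hypothesis 1 in Section 10.1 says that local signatures regulate later immunity. Among the planned groups, only Group F can link nasal to systemic measures in the same person, because Group C gives no blood and the other groups give no swabs. Section 10.1 also says the study is meant to supply initial estimates for designing later studies. A transcript that merely marks low prior immunity could be carried forward as a local determinant.

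**Working it through.** **The plan's own figure.** Section 10.2 gives 20 per age group by comparison with earlier studies. It states no alpha, power, effect size or correlation, so there is no calculation to reproduce.

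**Inputs.** n = 40 is the Group F maximum (Section 4). Everything else is assumed: two-sided 5%, and correlations with baseline from 0.3 to 0.7. Let B be Day 0 immunity, X the Day 1 nasal measure and Y the later response.

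**Step 1: no direct link between X and Y.** If B correlates at ρ with both, in the same direction, the expected correlation of X and Y is ρ × ρ = ρ². The chance of p<0.05 follows from Fisher's z: with z₀ = atanh(ρ²) × √(n − 3), it is Φ(z₀ − 1.96) + Φ(−z₀ − 1.96).

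At ρ = 0.5: ρ² = 0.25, and z₀ = 0.2554 × √37 = 0.2554 × 6.083 = 1.554. The chance is Φ(−0.406) + Φ(−3.514) = 0.342.

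**Step 2: adjustment for a perfectly measured B.** The partial correlation of X and Y given B is zero, so the rate returns to about 5%.

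**Step 3: adjustment for an imperfect marker of B.** With reliability λ, the partial correlation that remains is ρ²(1 − λ) / (1 − λρ²). At ρ = 0.5 and λ = 0.6 this is 0.25 × 0.4 / (1 − 0.15) = 0.10 / 0.85 = 0.118. With √(n − 4) = 6, z₀ = 0.709, and the chance is Φ(−1.251) + Φ(−2.669) = 0.109. Simulation gave 0.113.

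The unadjusted simulations (20,000 runs each) cover 40 people pooled and two centred strata of 20. The last column is for 40 people pooled.

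| Assumed ρ | Implied r | Unadjusted, Fisher | Unadjusted, simulated | Adjusted, perfect marker | Adjusted, reliability 0.6 (simulated) |
|---|---|---|---|---|---|
| 0.3 | 0.09 | 8.5% | 8.1-8.6% | about 5% | 5.7% |
| 0.4 | 0.16 | 16.6% | 16.6-16.7% | about 5% | 7.1% |
| 0.5 | 0.25 | 34.2% | 34.3-34.9% | about 5% | 11.3% |
| 0.6 | 0.36 | 63.0% | 63.0-64.4% | about 5% | 20.3% |
| 0.7 | 0.49 | 90.3% | 90.5-91.1% | about 5% | 40.6% |

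**Step 4: baseline acts only through the local response.** Let X have a true standardised effect of 0.4 on Y, let B correlate at size a with X, and give B no other path to Y. The unadjusted correlation is 0.4 and is not confounded. Its power is Φ(0.4236 × 6.083 − 1.96) = Φ(0.617) = 73%. The adjusted partial correlation is 0.4 × √[(1 − a²) / (1 − 0.16a²)]. At a = 0.5 it is 0.4 × √(0.75 / 0.96) = 0.354, which gives power Φ(0.370 × 6 − 1.96), or about 60%. At a = 0.3 and 0.7, adjusted power is about 68-69% and 45%.

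**The case against.** The strongest reply is that Section 2.2 is a sentence of rationale, not an analysis specification. The correlation is absent from the objectives (Section 3.1), Section 3.2 lists no T cell outcome, and Section 10.3 is silent. A reader might infer that the plan has fixed an unadjusted correlation as its method. The documents do not support that; they show an analysis left unspecified, in which baseline immunity has no stated role. This part of the objection stands.

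A reader might also infer that the protocol establishes prior immunity as a driver of both sides. It does not. The replication statement is introduced with a presumption, compares children with others, and is followed by an admission that the mechanisms are unclear. The effect on local crosstalk is only something to be examined. What remains is a plausible common cause, with some support in Group F's own age range from the remark on resident memory.

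The same text can be read as mediation: low prior immunity raises replication, and replication raises the later response. In that case adjustment removes no bias and costs power, as Step 4 shows. The documents do not settle which structure applies, though the account of the B cell response as recall of existing memory supports a separate baseline path for B cells.

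A transcript that stands in for low prior immunity still predicts later immunity. It misleads only if it is read as an independent local determinant. Finally, the study is declared exploratory and sets no significance threshold, so the rejection rates illustrate the bias rather than describe a decision rule in the plan.

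**Conclusion.** The gap is real and modest. Section 2.2 plans the association, no section gives Day 0 immunity a role in it, and the protocol's background makes prior immunity a plausible common cause. The unadjusted correlation alone cannot support the regulatory claim in hypothesis 1.

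The size of the bias is unknown. Under the assumptions above it is small at baseline correlations of 0.3 and becomes material from about 0.4 on both sides. The 5% figure after adjustment needs a perfectly measured baseline; with a marker of reliability 0.6, part of the bias stays.

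Two stronger readings should be set aside:
- The 34% at ρ = 0.5 is not the share of all transcripts that would be false. It is the chance of rejection for a transcript that has the assumed correlations.
- A reader might infer that a real local effect will be hidden. That requires baseline to act in opposite directions on the two sides, which the documents do not assert. Its size also depends on how the effect is defined. With opposing paths of 0.5, a standardised effect of 0.4 leaves r = 0.4 − 0.25 = 0.15, with power of 15% unadjusted against 64% adjusted. A partial correlation of 0.4 leaves r = −0.25 + 0.4 × 0.75 = 0.05, with 6% against 72%.

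This is a cheap improvement, not a flaw that undermines the study.

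**What to change.** In Section 10.3, specify the Group F association as a regression of the later response (for example log Day 28 HAI, or the Day 6-8 plasmablast or PPAb measure) on the Day 1 nasal transcript or viral level. Include log Day 0 HAI, Day 0 flu-specific cell measures where assayed, and age stratum as covariates.

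Report this beside the unadjusted correlation. Describe a transcript as a local determinant independent of prior immunity only if the adjusted association supports it. A transcript associated only without adjustment may still be reported as a predictor.

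The change is wording only, because Day 0 blood and baseline HAI are already planned. State the downsides with it:
- one degree of freedom for the Day 0 HAI term;
- loss of participants without Day 0 serum, since Section 7.2 takes a serum tube only for draws of at least 20 mL;
- residual confounding, because serum HAI misses resident memory and there is no Day 0 swab;
- some loss of power if baseline acts only through the local response (73% to about 60% in the Step 4 example).
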